2.8.1.1 Adverse events of special interest / grouping of AEs

AEs by primary system organ class and preferred term

The number and percentage of patients who reported treatment emergent adverse events will be summarized for each primary system organ class and preferred term. Primary system organ classes will be sorted alphabetically and, within each primary system organ class, the preferred terms will be sorted in descending order of frequency.

If a patient reported more than one adverse event with the same preferred term, the adverse event will be counted only once at the preferred term level. If a patient reported more than one adverse event within the same primary system organ class, the patient will be counted only once at the system organ class level.

Treatment emergent adverse events will be presented in two parts:

- Adverse events (including infections)
- Infectious adverse events

AEs by severity

All treatment emergent adverse events will be summarized by maximum severity for each primary system organ class and preferred term. If a patient reports more than one adverse event within the same primary system organ class, only one adverse event will be counted for that patient at the highest severity level in the total row for each primary system organ class. If a patient reported more than one adverse event with the same preferred term, the highest (maximum) severity will be presented.

AEs suspected to be related to study drug

The treatment emergent adverse events suspected to be related to the study drug (according to the investigators) will be summarized by primary system organ class and preferred term. Relationship to study drug is considered as suspected for those events where "Relationship to study drug" is answered by the investigator as "Suspected".

AEs leading to permanent study drug discontinuation

Treatment emergent adverse events leading to permanent study drug discontinuation will be summarized by primary system organ class and preferred term.

Serious Adverse Event (SAE)

Number and percentage of patients with serious adverse events, regardless of study drug relationship, will be presented by primary system organ class and preferred term.

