Taking into account the status of these ongoing studies at the date of May 2016, we may anticipate that a maximum of 8 patients included in CACZ885N2301 (within 4 French centers) may be included in CACZ885GFR01 from November 2016 and that a maximum of 21 patients included in CACZ885G2306 (within 3 French centers) from October 2016.

The last visit of study CACZ885N2301 will be the first visit of study CACZ885GFR01. Patients will continue on their last dosing regimen of the open-label long term treatment epochs (Epochs 4) considered to constitute the lowest clinically efficacious doses to maintain clinical efficacy in individual patients. Patients may receive an up-titration if they re-flare (maximum dose of 300 mg/ 4 mg/kg for patients weighing ≤ 40 kg) q4w.

The follow-up of patients with Hereditary Periodic Fever will be the same as the one for patients with SJIA.

The last visit of study CACZ885G2306 will also be the first visit of study CACZ885GFR01. Patients will continue on their dosing regimen considered to constitute the lowest clinically efficacious dose to maintain clinical efficacy in individual patients.

The study duration of CACZ885GFR01 study will be extended until canakinumab (Ilaris[®]) is commercially available for all indications.

Changes to the protocol are related to the following sections:

- Section 1.1. Background
- Section 1.2. Purpose
- Section 3.1. Study design
- Section 3.3. Rationale of dose/regimen, route of administration and duration of treatment
- Section 3.5. Risks and benefits
- Section 4. Population
- Section 5. Treatment
- Section 6. Visit schedule and assessments
- Section 9.4. Analysis of variables

Amendment 2

The purpose of this study CACZ885GFR01 is to provide continuous Ilaris[®] (canakinumab) treatment to patients in France who completed Study CACZ885G2301E1 (long term phase III study) until this medication is commercially available and reimbursed in France for the systemic Juvenile Idiopathic Arthritis indication. The current version of the protocol stipulates that the treatment period will be a maximum 12 months or could end sooner if Ilaris[®] was commercially available in France.

Because it is anticipated that the reimbursement of Ilaris[®] (canakinumab) may not be achieved at actual date of study completion, the study duration will be extended (one year extension).

Changes to the protocol are related to the following sections:

- Section 1.1. Background
- Section 1.2. Purpose
- Section 3.1. Study design

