1.1 Background

Systemic Juvenile Idiopathic Arthritis (SJIA) is a subset of Juvenile Idiopathic Arthritis (JIA), a serious and potentially disabling form of arthritis that occurs in children 16 years of age and younger, and accounts for approximately 4 - 17 % of JIA (Quartier 2007, Ravelli and Martini 2007). In contrast to other JIA subtypes SJIA is associated with systemic symptoms such as fever, rash, anemia, leukocytosis, elevated erythrocyte sedimentation rate and acute-phase. The peak age of disease onset lies between 18 months and 2 years, but SJIA may occur in children of any age and, rarely, in young adults too (Woo 2006).

Several lines of evidence show that interleukin-1 (IL-1) plays a pivotal role in the pathogenesis of SJIA (Dinarello 2005, Pascual et al 2005).

Ilaris[®] (Canakinumab) is a human monoclonal anti-human interleukin-1 beta (IL-1 beta) antibody of the IgG1/ κ isotype. Canakinumab binds with high affinity specifically to human IL-1 beta and neutralizes the biological activity of human IL-1 beta by blocking its interaction with IL-1 receptors, thereby preventing IL-1 beta-induced gene activation and the production of inflammatory mediators. Canakinumab has a half-life of approximately 21-28 days.

To date, four clinical studies (CACZ885A2203, CACZ885G2305, CACZ885G2301, and CACZ885G2301E1) have been performed by Novartis to evaluate canakinumab as a treatment for patients with SJIA.

Ilaris[®] received Marketing Authorization by the EMA for patients with Systemic Juvenile Idiopathic Arthritis (SJIA) on August 2013 for *the treatment of active Systemic Juvenile Idiopathic Arthritis (SJIA) in patients aged 2 years and older who have responded inadequately to previous therapy with non-steroidal anti-inflammatory drugs (NSAIDs) and systemic corticosteroids. Ilaris[®] can be given as monotherapy or in combination with methotrexate.*

Study CACZ885G2301E1 is a Phase III study designed to assess long-term safety and efficacy data for patients with SJIA who either participated in the CACZ885G2305 and CACZ885G2301 registration studies or were treatment-naïve to canakinumab. In France, 48 patients were enrolled in the CACZ885G2301E1 study at four centers (Necker, Kremlin- Bicêtre, Lyon, and Strasbourg). Study CACZ885G2301E1 is ending on November 2014 and 3 sites (Necker, Kremlin-Bicêtre, and Lyon) still have patients under treatment.

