The first French patients included CACZ885N2301 will complete the study from November 2016. According to amendment 3, patients who have benefited from canakinumab treatment will then be enrolled in the French CACZ885GFR01 study.

► Study CACZ885G2306 in SJIA

Study CACZ885G2306 has been requested by EMA and designed to assess 2 different canakinumab taper regimens in patients with SJIA with clinical remission on canakinumab treatment (inactive disease for at least 24 continuous weeks) without concomitant CS or MTX. Data from this study will be used to help guide physicians regarding canakinumab dose reduction in appropriate SJIA patients.

Eligible patients were entered Study Part I during which all patients were treated with canakinumab 4 mg/kg every 4 weeks until they qualify and enter Part II of the study.

Patients who become eligible for randomization enter the Study Part II and undergo canakinumab tapering (to receive canakinumab at either a reduced dose or a prolonged dose interval). Part II is a 72-week randomized treatment / follow-up period (48 weeks of canakinumab tapering followed by 24 weeks of follow-up while completely off-treatment).

Patients who do not become eligible for randomization may remain in Study Part I for the duration of the study, and since patients who fail any of the 3 canakinumab tapering steps during Part II may remain in Study Part II for the duration of the study, both study parts have been assigned an estimated maximum duration (for a given patient) of 216 weeks).

The study population consists of male and female patients aged ≥ 2 to < 20 years in two cohorts:

Cohort 1: Patients previously participating in Study CACZ885G2301E1 who at the time of evaluation for participation in CACZ885G2306 were treated with canakinumab 4mg/kg and had inactive disease

Cohort 2: Patients, who at screening had active SJIA and were canakinumab treatment-naïve.

A total of 172 patients have been enrolled (25 patients were enrolled in 3 French centers).

The objective of CACZ885GFR01 study is to collect additional safety data (serious and non-serious adverse events) and provide continuous canakinumab treatment for patients completing studies CACZ885G2301E1, CACZ885N2301 or CACZ885G2306 in France pending reimbursement of canakinumab (Ilaris®) in these indications.

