The study duration will depend on the date of reimbursement of canakinumab (Ilaris[®]) in France for the new indications and will be extended until the medication is commercially available for each indication. However, as the commercialization of the different indications may be effective at different dates, the patients will discontinue indication by indication (see section 5; end of treatment).

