9.4 Analysis of variables

9.4.1 Variables

a. Efficacy variables

There is no efficacy assessment in this study

b. Safety variables

Adverse events will be coded using the MedDRA dictionary that provides the primary system organ class and preferred term information. Adverse events will be presented in two parts:

- Adverse events (including infections)
- Infectious adverse events

Adverse events will be summarized for each disease by presenting the number and percentage of patients having any adverse event, having any adverse event in each primary system organ class and having each individual adverse event based on the preferred term. All other information collected (e.g. severity, relationship to study drug, or microorganism for infectious adverse events) will be tabulated and listed as appropriate.

Deaths, serious adverse events, and adverse events leading to discontinuation of study drug will be summarized by primary system organ class and preferred term and listed.

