2.2.1 Subgroup of interest

All planned table will be repeated on following subgroup.

- Pathology: SJIA, HIDS/ MKD and FMF

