2.8.2 Deaths

All the deaths in the clinical database will be listed with the last dose date/visit, date of death and investigator-reported principal cause. Deaths occurring after the first dose of study treatment until 30 days after the date of last treatment will be summarized with numbers and percentages for safety set.

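### Cheap improvement: adverse events, SAEs and deaths are summarised only as numbers and percentages of patients, with no rate per patient-time, although length of follow-up will differ between and within the pathology tables

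*SAP*

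**What the plan says.** **Summary measure.** SAP 2.8.1.1: "The number and percentage of patients who reported treatment emergent adverse events will be summarized for each primary system organ class and preferred term". A patient counts once per system organ class and once per preferred term, and SAEs are also given as number and percentage of patients. SAP 2.8.2 says that deaths up to a fixed point, "until 30 days after the date of last treatment will be summarized with numbers and percentages for safety set". Protocol 9.4.1 agrees: "Adverse events will be summarized for each disease by presenting the number and percentage of patients having any adverse event". Neither document plans a rate per patient-time.

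**Tables.** SAP 2.2.1: "All planned table will be repeated on following subgroup", the groups being SJIA, HIDS/MKD and FMF.

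**Entry.** Protocol 1.1: "Study CACZ885G2301E1 is ending on November 2014"; those patients pass directly into this study. The Amendment 3 summary expects a "maximum of 21 patients included in CACZ885G2306 (within 3 French centers) from October 2016". Protocol 1.1 again: "The first French patients included CACZ885N2301 will complete the study from November 2016". Protocol 4.1 also admits G2306 patients who relapse later, with no time limit.

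**Exit.** Protocol 3.1: "as the commercialization of the different indications may be effective at different dates, the patients will discontinue indication by indication".

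**Exposure and window.** SAP 2.4.1 derives duration of exposure from first to last dose, less interrupted days, and tabulates it apart from the adverse events. SAP 2.8.1 counts AEs up to 7 days after the last dose, and SAEs up to 30 days.

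**The concern.** AEs and SAEs are the only outcome that the protocol collects (6.3, 6.4). The percentage of patients with at least one event rises with time observed. If two groups have the same underlying rate, the group followed longer shows the higher percentage. The tables will be laid out by pathology, so a reader will see such percentages together without knowing how much of a difference is follow-up. The same holds inside the SJIA table, which pools two parent studies whose patients enter about two years apart.

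What is at stake is how the safety results are read. No planned number becomes wrong.

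**Working it through.** The plan states no rate, sample size or event count on this point, so there is no figure of its own to reproduce. What follows is an illustration.

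**Inputs from the documents.** Entry: November 2014 (G2301E1), October 2016 (G2306) and November 2016 (N2301). Planned maxima for SJIA (protocol 4): 12 from G2301E1 and 21 from G2306, so 33.

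**Assumptions.** One constant first-event rate in all patients; no dropout; everyone enters at the earliest stated date; whole months. End dates are also assumed. March 2017 is the latest month named in the protocol and is not an end date.

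**Formula.** Expected percentage with an event = 1 − exp(−rate × months/12). Pooled SJIA = (12 × p[G2301E1] + 21 × p[G2306])/33.

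**March 2017, rate 0.5 per year.** Follow-up is 28, 5 and 4 months.
- G2301E1: 1 − exp(−0.5 × 28/12) = 0.689
- G2306: 1 − exp(−0.5 × 5/12) = 0.188
- Pooled SJIA: (12 × 0.689 + 21 × 0.188)/33 = 0.370
- Periodic fever: 1 − exp(−0.5 × 4/12) = 0.153

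Within the SJIA table, the two parent studies stand at 69% and 19%, which pooling hides.

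**Range.** Later common ends add 12 or 24 months to every group. Cells show periodic fever against pooled SJIA.

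| Rate per year | March 2017 | March 2018 | March 2019 |
|---|---|---|---|
| 0.1 | 3% v 10% | 12% v 19% | 21% v 26% |
| 0.5 | 15% v 37% | 49% v 62% | 69% v 77% |
| 1.0 | 28% v 55% | 74% v 83% | 90% v 94% |

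**Unequal exit, rate 0.5.** If only SJIA runs to March 2018 and periodic fever stops at March 2017, the figures are 15% against 62%. If only periodic fever runs on, they are 49% against 37%, and the order reverses.

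**Can the SAP 2.4.1 duration serve as denominator?** With dosing every 4 weeks and no interruption it equals f = (doses − 1) × 28 + 1 days; the event window is f + 7 or f + 30.
- 5 doses: f = 113. Shortfall 7/120 = 6% for AEs and 30/143 = 21% for SAEs.
- 31 doses: f = 841. Shortfall 7/848 = 1% and 30/871 = 3%.

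It falls short most where follow-up is short, and it contains no time to first event.

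**Precision.** Take 2 first events in 8 × 4/12 = 2.7 patient-years. The rate is 75 per 100. Exact Poisson limits for a count of 2 are 0.242 and 7.225, so the interval is 9 to 271. In 8 × 16/12 = 10.7 patient-years the rate is 19 (2 to 68).

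**The case against.** The strongest case against is that the study is single-arm and descriptive (protocol 9.4.2), with no hypothesis, primary endpoint or planned comparison of indications. Exposure is tabulated and, under SAP 2.2.1, repeated by pathology. Dose dates, AE start and end dates and deaths are listed by patient. With at most 40 or 41 patients (the protocol gives both), a reader could form a crude rate by hand. Under a common end the gap is small in patients: for 8 periodic-fever patients at 0.5 per year, (0.618 − 0.487) × 8 = 1.1 patients at March 2018 and (0.768 − 0.689) × 8 = 0.6 at March 2019. The added rates will be imprecise.

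Most of this stands, and it fixes the weight of the point: this is an improvement to reporting. It does not remove the gap. The exposure table gives no time to first event and stops at the last dose, while events count for 7 or 30 days more. Working rates out from listings is what a summary should spare the reader.

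Three stronger readings are tempting:
- A reader might infer that the percentages are wrong or biased. They are correct counts over the observed period.
- A reader might take the March 2017 gap as the expected one. The documents give no end date, and a later common end narrows it.
- A reader might think the rates need only dates already on file. Protocol 7.1 lists no date of worsening among the AE items, and protocol 5.5.9 lists no remission among the reasons for stopping, so some rules must be written around what the CRF holds.

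**Conclusion.** The point holds as a low-cost improvement. Both documents confine AEs, SAEs and deaths to numbers and percentages of patients, and the design makes follow-up unequal between pathologies and within SJIA. That follow-up will differ rests on the documents. By how much does not: the sizes depend on an assumed constant rate, no dropout, earliest entry dates and assumed end dates. At 0.5 per year and a common end, follow-up alone accounts for a gap of 22 percentage points at March 2017, 13 at March 2018 and 8 at March 2019; unequal exit can widen or reverse it. A rate per patient-time removes this effect only if the rate is roughly constant. With so few periodic-fever patients it will not show whether indications differ, and the plan does not set out to.

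**What to change.** Keep every planned percentage and the TEAE definition. In the SAP, add, overall and by pathology (with SJIA split by parent study if wanted), three items for any AE, infections, SAEs, AEs leading to discontinuation and deaths:
- patients with at least one event;
- patient-years at risk, censored at the first event;
- the first-event rate per 100 patient-years, with an exact Poisson 95% interval.

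Use one window for events and time within each rate:
- SAEs and deaths: first dose to last dose + 30 days.
- Non-serious AEs: first dose to last dose + 7 days.
- Rates that mix serious and non-serious events (any AE, infections, AEs leading to discontinuation): last dose + 7 days for both numerator and denominator. Footnote the patients whose only event is an SAE on days 8 to 30, because SAP 2.8.1 keeps them in the percentage.

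Do not use the SAP 2.4.1 duration as denominator.

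State, using only data that the CRF records, how the first-event time treats:
- off-treatment gaps in patients who stop and resume (protocol 5), since SAP 2.8.1 defines one window per patient;
- start dates that SAP 5.1.2 imputes to the day after treatment start, which leave almost no time at risk, and start dates with no year, which stay null;
- baseline AEs that worsen.

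The cost is SAP wording, programming of first-event times, and a few table columns. No new data are needed if the rules keep to what is recorded. The intervals will be wide in the periodic-fever groups, and a footnote should say that the rates are descriptive.

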2.8.2 Deaths

All the deaths in the clinical database will be listed with the last dose date/visit, date of death and investigator-reported principal cause. Deaths occurring after the first dose of study treatment until 30 days after the date of last treatment will be summarized with numbers and percentages for safety set.

2.8.3 Laboratory data

Baseline measurements for laboratory evaluations will be taken from the last visit of the CACZ885G2301E1, CACZ885N2301 or CACZ885G2306 study.

All laboratory parameter will be listed and summarized with standard descriptive statistics.

- All lab value by laboratory test category and parameter name
 - BIOCHEM (BUN, GLUC etc)
 - HEMA (BAS,EOS etc)
 - URINE (UGLUCST, USPGR etc)

2.8.4 Other safety data

Not applicable

2.8.4.1 ECG and cardiac imaging data

Not applicable

2.8.4.2 Vital signs

Not applicable

2.9 Pharmacokinetic endpoints

Not applicable

2.10 PD and PK/PD analyses

Not applicable

2.11 Patient-reported outcomes

Not applicable

2.12 Biomarkers

Not applicable

2.13 Other Exploratory analyses

Not applicable

2.14 Interim analysis

Not applicable

3 Sample size calculation

No sample size calculation was performed for this extension study which will include all eligible subjects who complete CACZ885G2301E1 or CACZ885N2301 study and meet the eligibility criteria.

4 Change to protocol specified analyses

Not applicable

5 Appendix

5.1 Imputation rules

5.1.1 Study drug

No imputation for study drug.

5.1.2 AE date imputation

AE date imputation is based only on a comparison of the partial AE start date to the treatment start date.

1. If the AE start date year value is missing, the date uncertainty is too high to impute a rational date. Therefore, if the AE year value is missing, the imputed AE start date is set to NULL.
2. If the AE start date year value is less than the treatment start date year value, the AE started before treatment. Therefore:
 - a. If the AE year is less than the treatment year and the AE month is missing, the imputed AE start date is set to the mid-year point (01JulYYYY).
 - b. Else if the AE year is less than the treatment year and the AE month is not missing, the imputed AE start date is set to the mid-month point (15MONYYYY).
3. If the AE start date year value is greater than the treatment start date year value, the AE started after treatment. Therefore:
 - a. If the AE year is greater than the treatment year and the AE month is missing, the imputed AE start date is set to the year start point (01JanYYYY).
 - b. Else if the AE year is greater than the treatment year and the AE month is not missing, the imputed AE start date is set to the month start point (01MONYYYY).
4. If the AE start date year value is equal to the treatment start date year value:
 - a. And the AE month is missing or the AE month is equal to the treatment start month, the imputed AE start date is set to one day after treatment start.
 - b. Else if the AE month is less than the treatment start month, the imputed AE start date is set to the mid-month point (15MONYYYY).
 - c. Else if the AE month is greater than the treatment start month, the imputed AE start date is set to the start month point (01MONYYYY).

Table 1-2: AE date imputation

	MON	MON < CFM	MON = CFM	MON > CFM
	MISSING			
YYYY MISSING	NULL	NULL	NULL	NULL
	Uncertain	Uncertain	Uncertain	Uncertain
YYYY < CFY	(D) = 01JULYYYY	(C) = 15MONYYYY	(C) = 15MONYYYY	(C) = 15MONYYYY
	Before Treatment Start	Before Treatment Start	Before Treatment Start	Before Treatment Start
YYYY = CFY	(B)= TRTSTD+1	(C) = 15MONYYYY	(A)= TRTSTD+1	(A)= 01MONYYYY
	Uncertain	Before Treatment Start	Uncertain	After Treatment Start
YYYY > CFY	(E)= 01JANYYYY	(A)= 01MONYYYY	(A)= 01MONYYYY	(A)= 01MONYYYY
	After Treatment Start	After Treatment Start	After Treatment Start	After Treatment Start
Before Treatment Start	Partial indicates date prior to Treatment Start Date			
After Treatment Start	Partial indicates date after Treatment Start Date			

Uncertain	Partial insufficient to determine relationship to Treatment Start Date
LEGEND:	
(A)	MAX(01MONYYYY,TRTSTD+1)
(B)	TRTSTD+1
(C)	15MONYYYY
(D)	01JULYYYY
(E)	01JANYYYY

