2.8.1 Adverse events (AEs)

Adverse events starting on or after the time of the first dose of study drug but not later than 7 days (30 days in the case of a SAE) after the date of last dose of study drug taken or those AE present at baseline with increased severity will be classified as a TEAE and will be included in all summaries. AEs which started and ended prior to baseline and AEs which started prior to baseline but whose severity does not change post baseline will not be included in treatment emergent adverse event. In addition, all the treatment emergent AEs will also be listed.

The by-patient listing includes, SOC/PT/Verbatim term, start date, end date, the severity of an AE, Seriousness, whether or not an AE is related to study drug, and whether or not it is a serious AE, action taken with study drug, outcome, duration, discontinue from study. Duration will be calculated as end date – start date +1 and for ongoing last visit date – start date +1.

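### The AE start-date rule in SAP 5.1.2 ignores the end date, so rule 4a can date an event after it ended, and events with no start year have no stated treatment-emergent status

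*SAP*

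**What the plan says.** SAP 5.1.2 opens by stating that "AE date imputation is based only on a comparison of the partial AE start date to the treatment start date". Two of its rules matter here.

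- Rule 4a: when the start year equals the treatment year and the month is missing or is the treatment-start month, "the imputed AE start date is set to one day after treatment start".
- Rule 1: "if the AE year value is missing, the imputed AE start date is set to NULL".

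Table 1-2 of the SAP labels both situations as uncertain in relation to treatment start.

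SAP 2.8.1 makes the start date the main test for a treatment-emergent event: "Adverse events starting on or after the time of the first dose of study drug but not later than 7 days" after the last dose (30 days for a serious event). Events that pass, or that were present at baseline and worsened, "will be classified as a TEAE and will be included in all summaries". The same section excludes "AEs which started and ended prior to baseline", and it lists the treatment-emergent events with a duration: "Duration will be calculated as end date" minus start date plus 1.

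SAP 2.8 says that all data are used in the safety analyses and that missing data are not imputed. Protocol 7.1 has the investigator record both start and end dates.

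**The concern.** For a partial date, the imputed start decides whether the event is treatment-emergent. In SAP 2.8.1.1 the tables by organ class and preferred term, by severity, by suspected relationship and by drug discontinuation are all restricted to treatment-emergent events. A rule that does not look at the end date can place onset after resolution. If the resolution was before first dose, 5.1.2 points to treatment-emergent and 2.8.1 points the other way. With no stated order between them, the programmer decides.

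The NULL rule leaves a gap of a different kind. A missing date cannot be compared with first dose, and the SAP does not say what then happens to the event. SAP 5.1.3 treats concomitant medication more fully: it uses an extra flag and, where that flag variable exists, gives a missing year a default date. Adverse events, the main safety data of this study, get neither.

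**Working it through.** **Inputs.** The imputation rules and Table 1-2 come from SAP 5.1.2, the TEAE definition and duration formula from SAP 2.8.1, and enrolment ceilings from the protocol synopsis (40 patients, 7 with periodic fever) and Protocol section 4 (41 and 8). The documents give no count of partial dates, so the dates below are assumed, with first dose T = 20 Mar 2015.

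**Is the rule consistent within 5.1.2?** The text rules and the table were coded separately and compared over every treatment-start day in 2015 and 2016 (731 days), 5 year values (missing, 2014 to 2017) and 13 month values (missing, 1 to 12): 731 × 5 × 13 = 47,515 combinations, with no mismatch. The rule can be run as written.

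**Duration under rule 4a.** The imputed start is T + 1, so for end date E the duration is E − (T + 1) + 1 = E − T. It is negative whenever the event ended before first dose, and zero when it ended on the day of first dose.

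| Recorded start | Recorded end | Imputed start | TEAE by start date | Duration (days) | TEAE with the fix |
|---|---|---|---|---|---|
| Mar 2015 | 10 Mar 2015 | 21 Mar 2015 | yes | −10 | no |
| 2015, no month | 15 Feb 2015 | 21 Mar 2015 | yes | −33 | no |
| Mar 2015 | 20 Mar 2015 | 21 Mar 2015 | yes | 0 | yes, start capped at 20 Mar |
| Feb 2015 | 10 Mar 2015 | 15 Feb 2015 | no | 24 | no |
| 2014, no month | 10 Jan 2015 | 1 Jul 2014 | no | 194 | no |
| year missing | 10 Mar 2015 | NULL | cannot be tested | none | no |
| year missing | 10 Jun 2015 | NULL | cannot be tested | none | yes |
| year missing | ongoing | NULL | cannot be tested | none | yes |

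The first two rows are the conflict. Each event ended before first dose and so must have begun before it. SAP 2.8.1 excludes both, yet the start date from 5.1.2 passes the start-date test. Rows four and five fall under rules 4b and 2a and are classified correctly. The mid-month and mid-year rules can also fall after an early end date (start Feb 2015, end 10 Feb 2015 gives 15 Feb and 10 − 15 + 1 = −4 days), but such an event stays before treatment start, so its TEAE status does not change. The classification problem is confined to rule 4a.

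**What a NULL start affects.** A program that selects start ≥ first dose would not select a NULL, so the event would leave the TEAE-based tables and the TEAE listing. The serious-event table is worded differently: "Number and percentage of patients with serious adverse events, regardless of study drug relationship", with no treatment-emergent condition. SAP 2.8.2 lists every death with no condition on an event start date.

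**Size of one misclassified patient.** 1/41 = 2.4% and 1/40 = 2.5% overall; 1/8 = 12.5% and 1/7 = 14.3% for all periodic-fever patients together. SAP 2.2.1 repeats the tables by pathology, which splits that group further, so one patient counts for at least 12.5 points there.

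**The case against.** The strongest reply is that 5.1.2 only supplies a date, while 2.8.1 defines a TEAE and already excludes events that ended before baseline. On that reading rule 4a does no harm, and the negative durations never reach a listing that shows treatment-emergent events only. This is a reasonable reading, but the SAP does not state it, and it does nothing for the zero duration when the event ends on the day of first dose.

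The situation should also be rare. Events count only after consent (Protocol 7.1), and consent and treatment administration share the inclusion visit, where the schedule in Protocol section 6 marks no adverse-event collection. Protocol 8.3 sends omissions back to sites as queries. This stands and limits the size, although SAP 2.8.1 itself provides for events at or before baseline. The percentages above would apply to any single-patient error, and the share of patients with any event does not move if the patient has another TEAE. That stands too.

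A reader might infer two stronger things. One is that the rule makes resolved pre-dose events treatment-emergent in general. The documents do not support this: only rule 4a is involved, and 2.8.1 contains a contrary exclusion. The other is that undated events vanish from every table. The SAP does not say so: it is silent on NULL starts, the serious-event table is not restricted to TEAEs, all deaths are listed, and SAP 2.8 says that all data are used.

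**Conclusion.** The point holds as a minor defect with two parts. Rule 4a can produce an impossible date, with onset after the recorded end, and for ends before first dose it conflicts with the exclusion in SAP 2.8.1 without a stated order of precedence. Events with no start year have no stated TEAE status, and the likely programming default would leave them out of the TEAE tables and listing. SAP 2.8, which rules out imputation, also contradicts 5.1.2 as it stands.

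Few events are likely, but their number cannot be derived from the documents. The size figures assume the planned enrolment ceilings and a patient with no other event in the same table row.

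**What to change.** In SAP 5.1.2 add:

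1. The exclusion in 2.8.1 is applied first: an event with an end date before first dose is not treatment-emergent, whatever its imputed start.
2. An imputed start may not be later than a known end date; if it would be, the end date is used.
3. An event with a missing start year counts as treatment-emergent when its end date is missing or on or after first dose, unless other recorded information shows that it began before baseline without worsening.

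Then reword SAP 2.8 so that its no-imputation statement allows for the date rules in 5.1.2.

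The cost is a few lines of text and code, using dates already collected and adding nothing for patients. The downside lies in item 3: as a conservative default it may count a few events that began before baseline. Listing the events classified by this default would let a reader see how many there are.
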